To determine the extent by which these problems affect daily life for the individual, we are including the Activity of Daily Living (ADL) questionnaire. This survey assesses standard areas of daily living to determine the number as well as the severity of the problem. This survey was designed such that patients with cognitive decline could still yield meaningful responses. This test determined normative values based on comparing a patient's baseline status to their overall score on the survey, which allows it to be sensitive to mild decline as well as severe decline in cognitive function. The test is scored by taking the total score of a patient and dividing by the number of items rated which allows the test to only measure deficits seen with activities that the patient regularly participates in. This test has a validated cut off points for determine positive results: 0-33% may indicate some impairment, 34-66% moderate impairment, 67+%: severe impairment.

Lumosity administered assessments:

1. Arithmetic Reasoning
2. Forward Memory Span
3. Reverse Memory Span
4. Digit Symbol Coding
5. Divided Visual Attention
6. Trail Making A
7. Trail Making B
8. Progressive Matrices

Then, randomization will occur to a treatment group, which will include online access to structure-oriented activities(Lumosity), and an active control group(online crosswords).

Intervention group: Participants assigned to the intervention/experimental group will undergo twenty training sessions over 10 weeks. In each session, they practice video games selected from Lumosity(<http://www.lumosity.com>), a web-based cognitive training platform that includes games designed with the purpose of improving the user's cognitive abilities (Stenberg et al., 2013). Games will be customized using an automated algorithm supplied by Lumosity, to determine performance in the various targeted skills, which include: task switching, logical reasoning, quantitative reasoning, response inhibition, numerical calculation, working memory, face-name recall, selective attention, spatial recall, spatial orientations, planning, and divided attention.

Game Name	Targeted Skill
Brain Shift	Task Switching
Brain Shift Overdrive	Task Switching
By the Rules	Logical Reasoning
Chalkboard Challenge	Quantitative Reasoning
Color Match	Response Inhibition
Disconnection	Task Switching
Disillusion	Task Switching
Division Storm	Numerical Calculation
Ebb and Flow	Task Switching
Face Memory Workout	Working Memory

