Familiar Faces	Face-Name Recall
Follow that Frog	Working Memory
Lost in Migration	Selective Attention
Memory Lane	Working Memory
Memory Match	Working Memory
Memory Match Overdrive	Working Memory
Memory Matrix	Spatial Recall
Moneycomb	Spatial Recall
Monster Garden	Working Memory
Pet Detective	Planning
Pinball Recall	Working Memory
Playing Koi	Divided Attention
Raindrops	Numerical Calculation
Rhyme Workout	Working Memory

River Ranger	Information Processing
Rotation Matrix	Working Memory
Route to Sprout	Planning
Star Search	Selective Attention
Tidal Treasures	Working Memory
Train of Thought	Divided Attention
Trouble Brewing	Divided Attention
Word Sort	Logical Reasoning

Lumosity has the ability to customize games based on the performance in five different cognitive domains. Based on the participants' performance on exercises testing speed, memory, attention, flexibility and problem solving, certain online games can be emphasized based on the needs of the patient. Of interest will also be the profile of cognitive deficits determined by the Lumosity screening process that may characterize the cognitive problems typically seen in patients with ruptured cerebral aneurysms. Based on prior literature, we will be focusing on games designed to improve divided attention, flexibility, problem solving and memory

The recommended interaction would be 2 hours per week for 10 weeks for a total training time of 20 hours over the course of the study.

Active control group: The attention control group uses a computerized crossword puzzle game. This game offers a choice between three puzzle sizes, three levels of complexity, and varying font sizes. It also includes optional help features such as filling in an unknown letter or word. There is, however, no progressive challenge to the user by either increased speed, visual field size, number of distractors, or degree of difficulty of target stimulus differentiation. Thus, the crossword puzzle program provides an appropriate, computerized attention control alternative to the active visual speed of processing training.

To facilitate rapid recruitment into the study, randomization stratification will not be performed. After 10 weeks, both groups will complete the assessments that were used at enrollment.

Research Methods and Procedures for Post SAH Memory Study

Recruitment and Screening:

Recruitment: Study participants will be recruited in the following ways:

- A. *Neurosurgery Clinic Setting:*

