 Those with a modified Rankin 0 or 1
 Baseline memory problem affecting daily life
 Home computer or tablet with internet access

Exclusion

Unable to read or speak English

Data Analysis:

Data will be analyzed by a Spearman rank-order correlation. Data will be compared by using the number of completed puzzles and the amount of time spent completing them with changes noted on the CLCE-24 and working memory questionnaires. The Spearman rank-order will be used to show a monotonic relationship with completing strategy orientated puzzle and reduction in memory symptoms.

Table of Expected Results

Testing	Baseline	Post Intervention	Controls
CLCE-24	Cognitive and Emotional complaints: 3.3	Cognitive and emotional complaints: 1	Cognitive and emotional complaints: 3
ADLQ	Total: 17/84 or 20%	Total: 10/84 or 11%	Total: 18/84 or 21%
Working Memory	Total: 34.5 Storage: 11 Attention: 14 Executive Function: 9	Total: 20 Storage: 6 Attention: 8 Executive Function: 6	Total: 32 Storage: 10 Attention: 14 Executive Function: 8

Estimated sample size: 108 subjects total.

For CLCE-24, a sample size of 50 patients per group (total of 100 patients) can provide 80% power to detect a difference of 2 in number of complaints between the two groups, with a significance level of 0.5 and using a two-sample t-test (two-sided). For the Working memory questionnaire, a sample size of 54 patients per group (total of 108 patients) will achieve 80% power to detect a difference of 12 points between the two groups, with a significance level of 0.5 and using a two-sample t-test (two-sided).

Data Collection:

Data will be collected at different time points in this study. Please refer to table 1 for further reference.

Week 1: Consent, enrollment, completion of three Redcap assessments and Lumosity assessments. Randomization. Intervention group will receive access to Lumosity and control will get access to crossword puzzles.

Weeks 2-9: Intervention group will be reminded to complete Lumosity games; active controls will be reminded to complete cross-word puzzles

Week 10: All subjects complete the three Redcap assessments, the Lumosity assessments. Study completed at this time.

Table 1.

Group	Week 1	Weeks 2-9	Week 10
Intervention			
CLCE24/Working memory/ADLs/Lumosity	X		x
Lumosity	x	x	X
Control			
CLCE24/Working memory/ADLs/Lumosity	X		X
Active control		x	X

*At 70 day assessment, patients will have a +/-10 day window to submit questionnaires.

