Data Analysis: The primary analysis should be comparisons between the two groups for the outcome measures. T test or Mann-Whitney test can be used for comparisons and regression analysis may be performed with adjustment of baseline characteristics.

Questionnaires

For the CLCE-24, Working Memory and Activities of Daily Living Questionnaire, please see Appendix A.

Processes and controls to ensure study integrity

A key differentiator in this study is the use of online consent, data acquisition and data analysis. A concern for data being collected in this fashion concerns sampling bias and construct validity. One might think that support groups and online social networks may not capture data from patients who are older and not as familiar with technology. However, as social media improves its user interface, greater numbers of older users are being engaged. We believe *Lumosity* represents one such solution to address this concern. With regard to construct validity, we have included a series of questions we will administer over the phone in the event subjects are not actual patients of our practice for whom we have been able to review the relevant history, physical examination and imaging findings. Users of targeted social network groups are likely to be a self-selected motivated group of individuals. The likelihood that individuals without a diagnosis of brain aneurysm would be a part of this targeted social network and participate in the study seems unlikely. We hope that the relatively larger size of the dataset relative to previously published single-center series can overcome the effect any erroneous outliers may have on biasing the data.

Suitability of investigator(s) and institution

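### Does the unlabelled Spearman correlation between puzzle use and symptom change threaten the trial's efficacy conclusion?

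*Combined protocol and SAP*

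**What the plan says.** Two sections are headed Data Analysis. The one after the Inclusion/Exclusion Criteria opens with "Data will be analyzed by a Spearman rank-order correlation". It continues "Data will be compared by using the number of completed puzzles and the amount of time spent completing them", set against changes on the CLCE-24 and the working memory questionnaire, and states the aim: "The Spearman rank-order will be used to show a monotonic relationship with completing strategy orientated puzzle and reduction in memory symptoms". It gives no rank (primary, secondary or exploratory) and no analysis population.

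The one after Table 1 says "The primary analysis should be comparisons between the two groups for the outcome measures". It offers a t test or Mann-Whitney test, with optional regression on baseline characteristics, and does not mention the correlation.

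The sample size paragraph rests on two-sample t-tests. For working memory, "a sample size of 54 patients per group (total of 108 patients) will achieve 80% power to detect a difference of 12 points".

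On exposure, the Study Plan says "Participants assigned to the intervention/experimental group will undergo twenty training sessions over 10 weeks" and adds "The recommended interaction would be 2 hours per week for 10 weeks". Under Data Collection, for weeks 2 to 9, "Intervention group will be reminded to complete Lumosity games; active controls will be reminded to complete cross-word puzzles".

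**The concern.** Read alone, the earlier Data Analysis section makes a correlation with post-randomisation behaviour look like the trial's analysis. The hypothesis is causal and the Background says the effect will be evaluated in a randomised study, but randomisation does not protect this correlation. The Lumosity arm has a set number of sessions and both arms are reminded, so differences in use within an arm largely reflect adherence. A trait such as motivation could raise both use and self-reported improvement with no training effect.

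The unnamed arm adds a second difficulty. Lumosity tasks are games, while the control arm does crosswords whose size and complexity the participant chooses. A count pooled over both has no clear unit, and the resulting correlation could depend on which arm's items happen to be more numerous.

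At stake is a significant correlation being presented as evidence of efficacy.

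**Working it through.** **1. Which analysis the trial is built on.** Inputs: difference 12 points and 54 per group (sample size paragraph); SD 22.1 for brain-injured patients (Assessments, Working memory), assumed to be the sizing SD; 80% power, two-sided.

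n per group = 2 × (1.960 + 0.842)² × (22.1/12)² = 2 × 7.849 × 3.392 = 53.2, so 54.

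The t-distribution version gives 54.2, and power at 54 per group is 79.8%. This takes the printed significance level of 0.5 as 0.05; at 0.5 the answer would be 16. The stated figure is thus reproduced by the between-group comparison. No power is given for the correlation.

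**2. Rank.** One section names the group comparison as primary, and the sample size agrees with it. The correlation is therefore non-primary. Only the word secondary or exploratory is missing.

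**3. Arm.** The stated aim is limited to strategy-type puzzles. The Study Plan describes Lumosity as structure-oriented, and says the crosswords offer no progressive challenge. The natural reading is a use-response analysis within the Lumosity arm. This is not conclusive, because puzzle is also the word used for the control task. Nothing in the documents proposes pooling.

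**4. What pooling would do if someone did it.** Assume equal arms, normal use and improvement, and no use-response relation within either arm. For large samples:

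rho = 3 × (Px − 0.5) × (Py − 0.5)

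Here Px and Py are the probabilities that a Lumosity participant exceeds a control on use and on improvement. With 12/22.1 = 0.543, Py = Φ(0.543/√2) = 0.6495. SD 22.1 is here also assumed for change, which corresponds to a baseline/follow-up correlation of 0.5.

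| Use in Lumosity arm minus control | Px | rho by formula | Simulated mean, n = 108 |
|---|---|---|---|
| None | 0.5 | 0 | 0.00 |
| 1 SD | 0.760 | 3 × 0.260 × 0.1495 = 0.117 | +0.117 |
| Complete separation | 1 | 3 × 0.5 × 0.1495 = 0.224 | +0.226 |

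Reversing the difference reverses the sign (simulated −0.116 and −0.224). With an assumed SD of change of 14.0, complete separation gives about ±0.34. The unit problem applies to counts only. The plan also uses time spent, which has the same unit in both arms.

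**5. Confounding within one arm (n = 54, no training effect).** Assume a latent trait correlating r with both use and improvement. In 10,000 simulated trials per case:

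| r | Mean rho | Significant at 0.05 |
|---|---|---|
| 0 | 0.00 | 4.8% |
| 0.2 | 0.04 | 5.6% |
| 0.3 | 0.09 | 9.4% |
| 0.4 | 0.15 | 19.7% |
| 0.5 | 0.23 | 40.3% |

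The documents give no value for r. For r above zero these are not type I error rates, since the association is real; only a causal reading would be wrong.

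**6. Precision.** The rho detectable with 80% power is tanh(2.802 × √(1.06/(n − 3))): 0.38 for one arm of 54 and 0.27 for 108 pooled. Naming the arm therefore affects how informative the correlation is, but not the primary comparison.

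**The case for a change.** The best case for a change is that the omissions are real and a sentence would cure them. The later section settles what is primary, but not what the correlation is for, in whom it is run or what it may support. The earlier section is unqualified, and its stated purpose is to show a relationship with fewer symptoms. Two competent analysts could run different analyses. The outcomes are self-reported, and the section on study integrity itself describes social-network recruits as self-selected and motivated, so confounding by motivation is plausible.

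Much of this stands. The text has no label and no arm, and the correlation cannot support efficacy. What does not stand is the step to a defect in the plan. The wording claims a monotonic relationship, not an effect of treatment. The motivation remark is made to argue that people without an aneurysm are unlikely to enrol; it does not say that motivation varies with use or improvement, and a uniformly motivated group would be less confounded by it. The large pooled values depend on an analysis nobody proposes. Splitting by arm also has a cost: two use measures, two outcomes and two arms make 2 × 2 × 2 = 8 correlations instead of 4, each on half the sample.

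**Conclusion.** This is a gap that analysts fill sensibly. The correlation is a legitimate use-response description, subordinate to a between-group comparison that the plan names as primary and sizes at 54 per group. A careful analyst would run it within the Lumosity arm (and perhaps separately within the crossword arm), call it exploratory and draw no causal conclusion from it.

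The effect on the primary result is nil: no efficacy estimate, sample size or error rate moves. The remaining risk is misreading in a report, and the documents do not allow it to be sized. The pooled range of 0 to about ±0.22 (±0.34 with SD 14.0) and the 5.6% to 40.3% rates for r from 0.2 to 0.5 rest on assumed separations, SDs and latent correlations. The conclusion depends on the text, not on those figures. It would differ if the correlation were named as the primary analysis or used to judge efficacy, and the plan does neither.

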1. CLCE-24

This questionnaire was originally designed to be a diagnostic instrument for clinicians treating patients after a subarachnoid hemorrhage. This questionnaire addresses the most common cognitive and emotional complaints for patients who have experienced a subarachnoid hemorrhage highlighting the number of unresolved sequelae from a subarachnoid hemorrhage. The average number of complaints in this survey is 3.3 with 2.3 from cognitive and 1 from emotion problems. This study does not have a normal value but rather it was found that those that score higher were found to correlate with significantly lower CAMCOG (a standardized instrument for the diagnosis and grading of dementia) and MMSE (Mini-mental status exam) scores compared to those without complaints. This questionnaire shows no significant differences in scoring regardless for age, gender or education.

2. Working memory

This questionnaire was developed to assess the different areas of working memory including attention, executive function and working memory allowing patients to self-report their problems, which is beneficial for this patient population due to the awareness of their memory deficits. This questionnaire was developed for patients who had TBI, ischemic or hemorrhagic strokes. This survey allows us to not only assess what aspect of working memory is affected but also allows us to grade the severity. The test divides each question in to the sub-section it is testing and allots 40 points per section or 120 total. The average score of healthy individuals is 17.8 (SD:11.5) whereas, those with brain injury 34.5 (SD: 22.1)

3. Activity of Daily Living

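### Both power statements print the significance level as 0.5, almost certainly meaning 0.05, and the analysis paragraphs state no threshold

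*Combined protocol and SAP*

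**What the plan says.** The sample-size paragraph, in the first Data Analysis section below the table of expected results, contains two power statements.

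- CLCE-24: 50 patients per group "can provide 80% power to detect a difference of 2 in number of complaints between the two groups".
- Working Memory: "a sample size of 54 patients per group (total of 108 patients) will achieve 80% power to detect a difference of 12 points".

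Each continues "with a significance level of 0.5 and using a two-sample t-test (two-sided"). The overall target of 108 comes from the Working Memory statement (2 × 54).

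Neither statement names an SD. Under Assessments, the Working Memory description gives one: "those with brain injury 34.5 (SD: 22.1"), against 11.5 in healthy people. The CLCE-24 description gives only a mean: "The average number of complaints in this survey is 3.3 with 2.3 from cognitive and 1 from emotion problems".

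The documents describe the analysis in two places. The first Data Analysis section specifies a Spearman rank correlation. The second, after Table 1, says "The primary analysis should be comparisons between the two groups for the outcome measures", by t-test or Mann-Whitney test, with regression as an option. Neither gives a significance level.

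**The concern.** A two-sided level of 0.5 is not a credible design choice, and it appears twice in identical wording: "difference of 2 in number of complaints between the two groups, with a significance level of 0.5" and "difference of 12 points between the two groups, with a significance level of 0.5". If the sample size had really been computed at 0.5, the trial would be planned on an error rate ten times the usual one. If it was computed at 0.05, the printed figure is wrong.

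Nothing elsewhere corrects it. No threshold is prespecified for the final comparisons, so the only stated error rate is one that nobody should use. Read literally, it would make each null outcome significant half the time, and in favour of the intervention a quarter of the time. The reader is left to infer the operative level, which a prespecified plan should not require.

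**Working it through.** **Inputs**

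- Working Memory: difference 12, power 80%, 54 per group, two-sided two-sample t-test (sample-size paragraph). The 12 agrees with the table of expected results (32 − 20).
- Working Memory SD: 22.1 (Assessments, brain-injury sample). The power statement does not name it. The same line gives the mean of 34.5 that the table of expected results uses as the baseline, so it is the natural candidate.
- CLCE-24: difference 2, power 80%, 50 per group; no SD anywhere.

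**Step 1. Reproduce the stated 54 per group.** The standardised difference is d = 12 / 22.1 = 0.543, so d² = 0.2948. By the normal approximation, n per group = 2(z₁₋α/₂ + z₀.₈₀)² / d².

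- α = 0.05: 2 × (1.960 + 0.842)² / 0.2948 = 2 × 7.849 / 0.2948 = 53.2, rounded up to 54.
- α = 0.5: 2 × (0.674 + 0.842)² / 0.2948 = 2 × 2.299 / 0.2948 = 15.6, rounded up to 16.

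The exact calculation (noncentral t) agrees:

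| Two-sided α | n per group for 80% power | Power at 54 per group | SD at which 54 gives 80% |
|---|---|---|---|
| 0.05 | 54.2 | 79.8% | 22.05 |
| 0.5 | 14.6 | 98.4% | 42.7 |

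The α that gives exactly 80% power at 54 per group is 0.051. The SD implied at 0.05 (22.05) is almost the documents' own 22.1; the SD implied at 0.5 is nearly double it.

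**Step 2. Try other readings.** I varied α over 0.5, 0.1, 0.05, 0.025 and 0.01, one- and two-sided, with SD 22.1, 11.5 or their pooled value 17.62. None gives 54 at 0.5. One-sided 0.025 is the same calculation as two-sided 0.05, and the plan says two-sided. The only other near match is the pooled SD at two-sided 0.01 (53 per group), which is less plausible because it mixes in the healthy-population SD.

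**Step 3. What 0.5 would mean as a test threshold.** The smallest significant observed difference is t(1−α/2, 106 df) × 22.1 × √(2/54), where 22.1 × √(2/54) = 4.253.

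- α = 0.05: 1.983 × 4.253 = 8.4 points.
- α = 0.5: 0.677 × 4.253 = 2.9 points.

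**Step 4. CLCE-24.** With no SD, the 50 per group can only be solved backwards. It implies an SD of 3.53 at α = 0.05 or 6.85 at α = 0.5, and the documents cannot distinguish the two. At the 54 per group actually planned and α = 0.05, power depends on the assumed SD:

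| Assumed SD | 3 | 3.5 | 4 | 5 |
|---|---|---|---|---|
| Power | 93% | 84% | 73% | 54% |

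Power reaches 80% only if the SD is at most about 3.7.

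**The case against.** The best reply is that this is a dropped zero. The Working Memory size was evidently computed at 0.05, 108 is sound on that basis, and no analyst would test at 0.5. The figure appears only in the sample-size sentences, and nothing says it is the test threshold. The 50% false-positive rate and the 2.9-point cut-off are therefore hypothetical. I accept that, and they should not carry the weight of the point. What remains is that the only error rate in a combined protocol and SAP is wrong by a factor of ten and no correct one is stated.

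Three smaller objections are fair:

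- For CLCE-24, the misprint is inferred from the identical wording, not from arithmetic. The inference is reasonable, but the sponsor should confirm it.
- Under the exact t-test, 54 per group gives 79.8% and 80% needs 55. The stated 54 matches the normal approximation, and 79.8% rounds to the stated 80%.
- A sentence setting 0.05 for each comparison could be read as settling multiplicity. With three questionnaires, no single primary outcome and, for illustration, independent tests, the chance of at least one false positive is 1 − 0.95³ = 14%. That is a separate question.

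**Conclusion.** The concern holds and must be fixed. The significance level is wrong as printed in both power statements, and no usable threshold is prespecified for the final comparisons. For Working Memory, the stated size and power reproduce at two-sided 0.05 (54.2 per group; 79.8% power at 54) and not at 0.5 (14.6 per group; 98.4% power). This rests on 22.1 being the SD used, which the near-exact implied value of 22.05 strongly supports. For CLCE-24, the correction to 0.05 rests on the parallel wording, and the power claim cannot be verified at any level until an SD is given. The error does not undermine the Working Memory sample size.

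**What to change.** 1. In both power statements, change 0.5 to a two-sided significance level of 0.05.
2. In the second Data Analysis paragraph (after Table 1), add: *Each between-group comparison will be tested at a two-sided significance level of 0.05.* This sets the per-test level only; it leaves multiplicity across outcomes open. If the Spearman analysis is to be tested, its level should be stated too.
3. In the Working Memory statement, cite the SD of 22.1 from the brain-injury sample, once the sponsor confirms that it was the value used.
4. In the CLCE-24 statement, give and source the SD actually used and restate the power from it at 0.05. The back-solved 3.5 should not be entered as that SD.

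The cost is text only: two corrected numbers, one added sentence, an SD for each power statement and a restated CLCE-24 power. Conduct does not change, and the total of 108, set by Working Memory, stays. If the sourced CLCE-24 SD exceeds about 3.7, the restated power at 54 per group will be below 80%, and the plan should report that figure openly.

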 1. Study staff will be utilizing REDCap’s randomization tool. The randomization tool has been formatted to randomize patients into one of two groups, “Lumosity” or “active control”. **Stratification factors will include age (<50, 50 or older), gender, level of education (greater than high school education or not) and time since rupture of the aneurysm (<6 months or 6-12 months).** Randomization by the study staff will occur when the participant completes the demographic survey. This tool will help the study better implement a defined randomization model and allow the study staff to randomize participants easily.

[figure not shown]
Screen shots of the Project’s Randomization Tool:

b. Delivery of patient surveys

1. Surveys (CLCE-24, Working Memory, and Activities of Daily Living ADL Scale) will be sent to participants via the REDCap system. Study participants will be able to complete all surveys and submit them online. Individual emails are sent out to each person in the study. The email will contain brief instructions about completing the survey and a secured link to their individual survey queue.

Screen shot of the Survey Queue:

c. Collection of Survey Responses:

1. The REDCap database will alert the study team on which surveys were and were not completed by specific participants. The study staff will be able to send reminders to those who have not yet completed all the required surveys in their queue.

Screen shot of the participant list:

Participant List belonging to [Initial survey] "Information about you" Remove all participants

Displaying 1 - 7 of 7 Add participants Compose Survey Invitations Export list

Email	Participant Identifier	Responded?	Invitation Scheduled?	Invitation Sent?	Link	Survey Access Code	Survey Queue
[No email listed]	Disabled		-				remove
[No email listed]	Disabled		-				remove
[No email listed]	Disabled		-				remove
[No email listed]	Disabled		-				remove
[contact]	Disabled		-		-	-	
[contact]	Disabled		-				remove
[contact]	Disabled		-		-	-	

d. Data Export

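### Working Memory questionnaire: the total of 108 equals the number the t-test must analyse, so the stated 80% power holds only if essentially everyone provides Week 10 data

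*Combined protocol and SAP*

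**What the plan says.** The planned total is given as "Estimated sample size: 108 subjects total". The same paragraph holds two power statements. CLCE-24 is said to need 50 per group (100 in all) to detect a difference of 2 complaints. The Working Memory statement reads "a sample size of 54 patients per group (total of 108 patients) will achieve 80% power"; its target is a 12-point difference. Both are described "with a significance level of 0.5 and using a two-sample t-test (two-sided"). The Working Memory calculation is the larger and therefore sets the total.

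The paragraph gives no SD. The description of the Working Memory questionnaire under Assessments reports "those with brain injury 34.5 (SD: 22.1").

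No loss rate, inflation factor or missing-data rule appears in the text available for review; one part of the document was not available. The Data Collection section has all subjects completing the assessments at Week 10, with a window of 10 days either side of day 70. Under Collection of Survey Responses, "The study staff will be able to send reminders to those who have not yet completed all the required surveys in their queue". The Data Analysis paragraph after Table 1 makes the between-group comparison primary, by t-test or Mann-Whitney test, and adds that "regression analysis may be performed with adjustment of baseline characteristics".

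**The concern.** The number of subjects planned and the number the t-test must analyse are the same figure. A calculation of this kind gives the power for the participants who contribute an outcome. If fewer than 54 per group return the Week 10 Working Memory questionnaire, power for that outcome is below the stated value.

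Some loss is plausible. Participants are selected for memory problems that affect daily life, some are recruited and consented remotely, they are asked for 10 weeks of home activity, and they return questionnaires through emailed links.

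What is at stake is how a null result is read. Readers would set it against 80% power when the power actually available may have been nearer 70%. Baseline scores on the same questionnaire are collected from everyone and could recover some of that power, but the plan does not commit to using them.

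**Working it through.** **Inputs**
- Difference 12 points, 54 per group, target power 80%, two-sided two-sample t-test: sample-size paragraph.
- SD 22.1: brain-injury value in the Working Memory description under Assessments. Using it in the power calculation is an inference, supported by the fact that it reproduces 54.
- Alpha 0.05: assumed in place of the printed 0.5 (step 2).
- Loss of 10%, 20% and 30%, equal in both groups: assumptions.
- Correlation r between baseline and Week 10 scores, 0.3 to 0.6: assumption.

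**1. Reproduce the plan's figure.** Standardised difference d = 12/22.1 = 0.543. By the normal approximation, n per group = 2 × (1.960 + 0.842)² × (22.1/12)² = 53.2, rounded up to 54. With the noncentral t distribution, the n for exactly 80% is 54.2. Power at 54 per group is 80.6% (normal) or 79.8% (t). The plan's figure is reproduced.

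**2. Check the printed alpha.** At two-sided 0.5 the same inputs need 2 × (0.674 + 0.842)² × (22.1/12)² = 15.6, or 16 per group, and 54 per group would give 98.4% power. So 54 per group with 80% power fits 0.05 and not 0.5.

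**3. Apply loss.** With analysed n = 54 × (1 − loss), the unadjusted t-test (noncentral t, alpha 0.05) gives:

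| Loss (assumed) | Analysed per group | Power |
|---|---|---|
| 0% | 54 | 79.8% |
| one per group | 53 | 79.1% |
| 10% | 48.6 | 75.5% |
| 20% | 43.2 | 70.4% |
| 30% | 37.8 | 64.4% |

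With 48 whole participants per group, the 10% figure is 75.0%.

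**4. CLCE-24.** The stated need is 100 and the plan has 108, so 108 − 100 = 8 participants (8/108 = 7.4%) can be lost, if spread evenly, before its stated 80% is reached. Its SD is not given. Back-calculating from 50 per group and 80% gives about 3.53. On that assumption power is 83.0% with no loss, 78.8% at 10% and 73.9% at 20%.

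**5. Baseline adjustment.** ANCOVA reduces the residual SD to 22.1 × √(1 − r²), so the effective standardised difference is 0.543/√(1 − r²). For r = 0.5 this is 0.543/0.866 = 0.627. Power for the Working Memory questionnaire:

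| Loss | r = 0.3 | r = 0.4 | r = 0.5 | r = 0.6 |
|---|---|---|---|---|
| 10% | 79.3% | 82.4% | 86.4% | 91.2% |
| 20% | 74.4% | 77.7% | 82.1% | 87.7% |

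At 30% loss and r = 0.5, power is 76.7%.

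**The case against.** **No loss rate is documented.** This stands: 10%, 20% and 30% are illustrations. The plan has reminders in Weeks 2-9, a submission window of 10 days either side, and expects motivated participants from social networks. The facility to remind people about uncompleted surveys limits loss; it does not forecast it. A reader might infer that the design as written lacks its stated power. The documents do not support that. 79.8% rounds to 80%, the normal approximation gives 80.6%, and any shortfall is conditional on loss occurring.

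**The plan has two power statements.** A reader might infer that any loss takes the whole design below 80%. That is not so: CLCE-24 has a reserve of 8, and the plan names no single primary outcome. The point is confined to the Working Memory questionnaire.

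**It is not stated whether 108 means randomised or analysed.** This stands as an ambiguity. Reading 108 as the number enrolled is reasonable, since all subjects are to complete Week 10, but it is an inference. The restatement proposed below removes the ambiguity on either reading.

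**Alpha and SD are substituted.** At the printed 0.5, power would still be about 97% at 20% loss, but that alpha does not yield the plan's 54. The SD matters as much as loss does: at an illustrative SD of 20, power is 83% at 10% loss and 79% at 20%; at SD 24 it is 73% with no loss. Both values therefore need to be written beside the power figure.

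**Adjustment is no guarantee.** A reader might infer that ANCOVA fully repairs the shortfall. That depends on r: at 20% loss it needs r of about 0.5, and r = 0.3 or 0.4 falls short of 80%.

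**Conclusion.** The concern holds for the Working Memory questionnaire, conditional on loss. The planned total carries no reserve over the number the t-test needs. The stated 80% is therefore the power with essentially complete Week 10 data, and one lost participant per group gives 79.1%. At the assumed losses the deficit against 80% is about 5, 10 and 16 percentage points. These figures rest on SD 22.1, alpha 0.05, equal loss in the two groups and an unadjusted t-test. They do not show that the trial is underpowered if follow-up is complete, and they do not carry over to CLCE-24. Baseline adjustment would offset part or all of the deficit, by an amount the documents cannot settle.

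**What to change.** 1. In the sample-size paragraph, correct the printed significance level and replace the Working Memory sentence with: *54 participants per group with Week 10 data give about 80% power for a 12-point Working Memory difference (SD 22.1, two-sided alpha 0.05, unadjusted t-test); with 10%, 20% or 30% loss, power is about 75%, 70% or 64%.* Add that CLCE-24 needs 100 and so allows for 8 losses.

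2. In the Data Analysis paragraph after Table 1, make the primary analysis the between-group comparison of the Week 10 score adjusted for the baseline score on the same questionnaire (ANCOVA), in place of optional regression. State the assumed baseline-to-Week-10 correlation, or a range, whenever power for this analysis is quoted.

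Cost: a slightly less favourable stated power and a small change to the analysis plan, which should be made before outcome data are seen. Enrolment and data collection do not change. If the sponsor instead wished to keep 54 completers per group under the unadjusted test, enrolment would have to rise to 54/0.9 = 60 per group at 10% loss or 54/0.8 = 67.5, so 68, per group at 20%. The fix above does not require that, but it also does not guarantee 80%.
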